8.8 HEALTH ECONOMICS

Health Economics parameters will not be evaluated in this study.

8.9 TIMING OF STUDY ASSESSMENTS

8.9.1 Screening and Pretreatment Assessments

Written informed consent for participation in the study must be obtained before performing any study-specific screening tests or evaluations. Informed Consent Forms (ICFs) for enrolled patient and for patients who are not subsequently enrolled will be maintained at the study site.

All screening and pre-treatment assessments must be completed and reviewed to confirm that patients meet all eligibility criteria. The Investigator will maintain a screening log to record details of all patients screened and to confirm eligibility or record reasons for screening failure.

An Eligibility Screening Form (ESF) documenting the Investigator's assessment of each screened patient with regard to the protocol's inclusion and exclusion criteria is to be completed by the Investigator and kept at the investigational site.

Screening and pre-treatment assessments will be performed as described in the SoA (see Section 1.2). Results of standard-of-care tests or examinations performed prior to obtaining informed consent and within 72 hours prior to first dose may be used (and do not need to be repeated for screening).

8.9.2 Assessments during Treatment

Under no circumstances will patients who enroll in this study and have completed treatment as specified, be permitted to be allocated a new enrollment number and re-enroll in the study.

All assessments must be performed as per SoA (see Section 1.2). Assessments scheduled on the day of study treatment administration should be performed prior to administration of study treatment, unless otherwise noted in the schedule of assessments. COA assessments should be performed prior to the completion of other study assessments.

8.9.3 Assessments at Study Completion/Early Termination Visit

Patients who discontinue from the study for any reason will be asked to return to the clinic to complete an End-of-Study (EOS) visit 28 days after the last dose.

If discontinuation is due to progression of disease, the EOS visit should be completed on the day the response assessment shows progressive disease instead of the next scheduled visit. See Section 1.2 for the assessment to be performed at the study completion visit.

8.9.4 Follow-Up Assessments

After the study completion/early termination visit, adverse events should be followed as outlined in Sections [8.3.1](#) and [8.3.2](#).

8.9.5 Assessments at Unscheduled Visits

Assessments as listed in Section [1.2](#) as deemed necessary by the Investigator and/or Sponsor, in particular for safety, will be performed at unscheduled visits.

8.9.6 Patient Engagement Application

The Smartphone Patient Engagement Application is an optional service that patients can opt-in to use to remind them of activities/tasks relevant to study compliance, e.g., attend study visits. The application also provides supportive guides to help patients to be aware of visit procedures, study information and instructions. Additional details are found in [Appendix 13](#).

9. STATISTICAL CONSIDERATIONS

The data will be listed and summarized with respect to demographic and baseline characteristics, efficacy observations and measurements, safety observations and measurements, and PK and biomarker measurements. No formal hypothesis testing is planned in the study. All the analyses will be descriptive.

9.1 STATISTICAL HYPOTHESES

This section is not applicable.

9.2 SAMPLE SIZE DETERMINATION

9.2.1 Sample Size in Ruxolitinib-Naïve Patients

Approximately 20 efficacy-evaluable patients without prior ruxolitinib exposure will be enrolled.

For 12 patients who are ruxolitinib-naïve with splenomegaly, observing a composite response rate of 50% (6/12) would provide a posterior probability of 85% that the true rate is greater than a 35% response rate. A 35% composite response rate is the minimum response rate to be considered of interest ([Vannuchi et al. 2015](#)).

Assuming a true composite endpoint rate of 60%, there is an 84% probability of observing at least 6 responders out of 12 patients.

In 20 ruxolitinib-naïve patients, observing a Hct control rate of 70% (14/20) would provide a posterior probability of 80% that the true rate is greater than 60%. Assuming a true Hct control rate of 75%, there is a 79% probability of observing at least 14 responders out of 20 patients.

Based on the results from *the trials RESPONSE and RESPONSE-2* in patients *with and without splenomegaly*, a 60% Hct control rate is the minimum response rate to be considered of interest. For 8 patients who are ruxolitinib-naïve without splenomegaly, observing a Hct control rate of 75% (6/8) would provide a posterior probability of 79% that the true rate is greater than 60%. Assuming a true Hct control rate of 75%, there is a 68% probability of observing at least 6 responders out of 8 patients.

For all 20 ruxolitinib-naïve patients, observing CHR of 45% (9/20) would provide a posterior probability of 81% that the true rate is greater than 35%. Assuming a true rate of 50%, there is 75% probability of observing at least 9/20 responders. Up to 20 additional patients may be enrolled to confirm safety, efficacy, and/or PK.

9.2.2 Sample Size in Ruxolitinib-Resistant or Intolerant Patients

Approximately 20 efficacy-evaluable, ruxolitinib-resistant or intolerant patients will be enrolled in the initial phase of the study. Approximately 40 additional patients may be enrolled for further evaluation of safety and efficacy if warranted by results in the initial phase of the study and upon the discretion of the Sponsor, in a cohort expansion phase.

In this population, a Hct control rate of 30% is considered to be clinically meaningful. Observing a Hct control rate of 40% (8/20) would provide a posterior probability of 82% that the true rate is greater than 30%. Assuming a true Hct control rate of 40%, there is a 75% probability of observing at least 7 responders out of 20 patients.

From the initial phase, if the proportion of responders based on Hct control is above 30% in the ruxolitinib-resistant or intolerant cohort, the Sponsor may decide to enroll approximately an additional 40 patients with the goal of registration (expansion cohort), that would be considered the totality of available efficacy and safety data. The minimum sample size of 60 (40 patients from the expansion plus 20 patients from the initial phase) is expected to give sufficiently narrow confidence intervals. Based on a sample size of N = 60, the following table shows corresponding lower bounds of the two-sided 95% confidence interval for a range of potential observed response rates.

Table 9 *Lower Limit of Two-Sided 95% Confidence Interval for a Range of Potential Observed Response Rates based on a Sample Size of 60 Patients*

Observed Response Rate	Lower Limit of Two-Sided 95% Confidence Interval (exact Clopper-Pearson method)
35% (21/60)	23.1
40% (24/60)	27.6
45% (27/60)	32.1
50% (30/60)	36.8
55% (33/60)	41.6
60% (36/60)	46.5

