1.2 SCHEMATIC OF STUDY DESIGN

An overview of the study design is shown in Figure 1.

Figure 1 Overview of Study Design

**Patients without measurable splenomegaly at baseline ^spleen imaging at end C5 only if <35% reduction at end C3
 †to be evaluated in ruxolitinib naive patients ‡MPN-SAF-TSS, EORTC QLQ-C30, PGIC †Bone Marrow biopsy every 6 cycles post week 32 per PI discretion in context of ELN CHR response

Initial phase

Ruxolitinib Naïve patients (up to 20)

Ruxolitinib resistant or intolerant patients (up to 20)

If favorable benefit/risk

Expansion phase

Ruxolitinib resistant or intolerant patients (additional 40, in total n=60)

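### If the expansion opens, the pooled N=60 hematocrit-control rate is biased upward in expectation, because it includes the 20 patients whose result opened it; the expansion patients should also be reported alone

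*Protocol*

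**What the plan says.** Protocol 9.2.2 sets the first stage: "Approximately 20 efficacy-evaluable, ruxolitinib-resistant or intolerant patients will be enrolled in the initial phase of the study". It gives the reference rate: "In this population, a Hct control rate of 30% is considered to be clinically meaningful". It then makes the second stage depend on the first, under this condition: "if the proportion of responders based on Hct control is above 30% in the ruxolitinib-resistant or intolerant cohort". Meeting the condition permits expansion without requiring it, and the stated purpose is regulatory: "the Sponsor may decide to enroll approximately an additional 40 patients with the goal of registration (expansion cohort".

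The sample named for that goal is the sum of both stages: "The minimum sample size of 60 (40 patients from the expansion plus 20 patients from the initial phase". The study schema in Protocol 1.2 agrees: "additional 40, in total n=60". For precision, 9.2.2 says: "Based on a sample size of N = 60, the following table shows corresponding lower bounds of the two-sided 95% confidence interval". The column heading of Table 9 names the "exact Clopper-Pearson method".

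Neither document separates the two phases in the analysis:

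- Protocol 9.3 defines populations by ruxolitinib history.
- SAP 5.7.2.5 evaluates Hct control in all ruxolitinib-exposed patients together.
- The SAP response table RSPT01 (5.7.1) splits the exposed block by splenomegaly only.
- Protocol 9.5 states that no interim analysis is prospectively planned, so no two-stage estimate or interval is described.

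**The concern.** A 60-patient data set comes into being only if the first 20 patients did well enough. In the trials where it exists, their observed rate is high partly by selection, and one third of the pooled sample (20/60) carries that selection into the final figure. The other 40 patients are not selected on their own results.

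The analyses are descriptive, so the point estimate and its interval carry the evidence toward registration. The overstatement is largest when the true rate is at or below the protocol's own 30% reference, where the reading of the result is most delicate.

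**Working it through.** **Inputs (Protocol 9.2.2).** Initial phase n1 = 20; expansion n2 = 40; pooled N = 60; gate: observed rate above 30%; interval: two-sided 95% Clopper-Pearson; assumed true rate 40%; reference rate 30%.

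**Step 1. Reproduce the plan's figures.** The lower limit for x/60 is the 2.5% quantile of Beta(x, 61 − x). For 21, 24, 27, 30, 33 and 36 responders this gives 23.1, 27.6, 32.1, 36.8, 41.6 and 46.5, which is Table 9. P(X ≥ 7 | 20, 0.40) = 0.750, the stated 75%. Table 9 is therefore a correct single-stage calculation with no allowance for the gate.

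**Step 2. The gate.** 6/20 is exactly 30%, so a result above 30% means X1 ≥ 7.

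**Step 3. Mean of the pooled rate, given expansion.** With X1 ~ Bin(20, p) and X2 ~ Bin(40, p) independent:

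E[pooled | X1 ≥ 7] = (E[X1 | X1 ≥ 7] + 40p) / 60.

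Because E[X1 | X1 ≥ 7] > 20p for every p strictly between 0 and 1, the conditional bias is always upward. Two cases written out:

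- p = 0.30: E[X1 | X1 ≥ 7] = 8.053, so (8.053 + 12)/60 = 33.42%.
- p = 0.40: E[X1 | X1 ≥ 7] = 8.929, so (8.929 + 16)/60 = 41.55%.

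**Step 4. Lower-limit error.** Let L be the N=60 lower limit. Enumerate X1 + X2 exactly and sum the probability that L > p. At p = 0.30 this needs at least 26/60 (L = 30.6%; 25/60 gives 29.1%).

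| True p | P(expand) | Initial 20, mean given expansion | Pooled mean given expansion | Bias (points) | P(L > p), given expansion | P(expand and L > p), all trials |
|---|---|---|---|---|---|---|
| 25% | 0.21 | 38.8% | 29.59% | +4.59 | 5.7% | 1.2% |
| 30% | 0.39 | 40.3% | 33.42% | +3.42 | 4.5% | 1.8% |
| 35% | 0.58 | 42.2% | 37.40% | +2.40 | 3.8% | 2.2% |
| 40% | 0.75 | 44.6% | 41.55% | +1.55 | 1.8% | 1.3% |
| 45% | 0.87 | 47.7% | 45.90% | +0.90 | 1.6% | 1.4% |
| 50% | 0.94 | 51.4% | 50.46% | +0.46 | 1.5% | 1.4% |

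The nominal one-sided error is 2.5%.

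**Step 5. The other frame.** Over all trials, using X1/20 when the trial stops and the pooled rate when it expands, the mean is 27.3% at a true 30% and 37.7% at a true 40%. In that frame the bias is downward.

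**Step 6. Sensitivity to the gate.** Expansion also needs a Sponsor decision. If in practice that meant at least 8/20, the conditional bias would be +4.7 points at 30% and +2.5 at 40%, with lower-limit error of 6.8% and 2.2%.

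**Step 7. Alternatives.**

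- *Expansion patients alone.* X2/40 has no selection bias at any p and does not depend on where the gate sits. 16/40 has a 95% CI of 24.9% to 56.7%; 24/60 has 27.6% to 53.5%.
- *Conditionally unbiased estimator.* E[X2/40 | X1 + X2, X1 ≥ 7] uses all 60 patients. 21/60 (35.0%) becomes 32.2%, and 24/60 (40.0%) becomes 38.4%. Its mean given expansion equals p.
- *Ordinary two-stage UMVUE.* It equals E[X1/20 | X1 + X2, X1 ≥ 7] when the trial expands, so given expansion it has the mean of the selected first 20: 40.3% at a true 30%. It turns 21/60 into 40.6%. It corrects the downward bias of Step 5 and makes the conditional bias worse.

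**The case against.** The strongest reply has four parts.

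1. *Table 9 only illustrates precision.* It sits in a sample-size section. Protocol 9 and 9.4.2 plan no hypothesis test, 9.2.2 refers to the totality of efficacy and safety data, and no limit is set as a pass mark. This stands in part. A reader might infer that the N=60 lower limit is the registration criterion, and the documents do not say so. But it is the only sample and interval described for that goal, and bias in an estimate does not depend on a test being done.

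2. *Overall error is controlled.* A reader might infer an inflated false-positive rate. The documents do not support that: in the last column of the table the error is at most 2.2%. A reader might also infer that the estimate is biased upward in every sense, and Step 5 shows otherwise. What remains is the behavior of the pooled figure in the trials where it is reported.

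3. *The bias is small where the drug works.* This stands. At the assumed 40% it is about one and a half points, and the lower-limit error is below nominal. The 5.7% at a true 25% belongs to a scenario in which expansion opens about one time in five, and it counts limits above 25%, not above 30%.

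4. *The expansion result can be recovered by subtraction.* Protocol 9.4.2 triggers a primary analysis at 20 evaluable patients. But the trigger is 20 in either ruxolitinib group, so a report on exactly the initial 20 resistant or intolerant patients is not assured. Nor is an expansion-only interval planned.

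**Conclusion.** The point holds conditionally. Once the expansion opens, the pooled N=60 Hct control rate is biased upward in expectation; a single realized estimate can still fall below the truth. The size is about 3 to 5 points when the true rate is 25% to 30%, and 1.55 points or less from 40% upward. The lower-limit error given expansion is above nominal at 25% to 35% and below it from 40%.

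The figures assume exactly 20 and 40 evaluable patients, expansion at every result of 7/20 or more, and the same true rate in both phases. The protocol says approximately for both counts and leaves expansion to the Sponsor, so they are indicative; a stricter gate in practice would make the bias larger. The case for an expansion-only result does not rest on these details. This is an inexpensive improvement to reporting and does not invalidate the design.

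**What to change.** In Protocol 9.2.2, and in SAP 5.7.2.5 with table RSPT01, state that if the expansion opens, Hct control with its exact 95% CI will be reported for the expansion patients alone beside the pooled 60. Add a footnote that the pooled figure includes the patients whose result triggered the expansion. Settle this before expansion data exist, so that the choice of estimate is not made after seeing them.

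If an adjusted pooled estimate is wanted as well, specify the conditionally unbiased estimator given at least 7/20, with a matching conditional interval. This needs the gate to be stated as a firm rule. The ordinary two-stage UMVUE should not be used for this purpose, for the reason in Step 7.

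The cost is one table column and a few sentences. Enrollment, visits and treatment are unaffected. The expansion-only interval is wider: at an observed 40%, 31.8 points (56.7 − 24.9) against 25.9 for the pooled 60 (53.5 − 27.6). Both can be shown.

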9.3 POPULATIONS FOR ANALYSES

For purposes of analysis, the following *two main populations (and combined populations)* will be described as defined in [Table 10](#):

- *Ruxolitinib-naïve patients*
- *Ruxolitinib-resistant or intolerant patients*

Additional populations may be defined in the Statistical Analysis Plan (SAP).

Table 10 Analysis Populations for Ruxolitinib-Naïve and Ruxolitinib-Resistant or Intolerant Patients

Description Analyses Per Population and Combined Populations	
Efficacy	Primary efficacy population consists of patients who have completed at least 32 weeks of treatment or withdrew prior to Week 32 due to NR or progressive disease. There will also be an early-look efficacy population consisting of patients who have completed at least 3 and/or 5 cycles.
Safety	All patients who received at least one dose of the study treatment, whether prematurely withdrawn from the study or not, will be included in the safety analysis.
PK	All patients who have received at least one dose of study treatment and who have data from at least one post-dose sample will be included in the PK analysis population. Patients will be excluded from the PK analysis population if they significantly violate the inclusion or exclusion criteria, deviate significantly from the protocol, or if data are unavailable or incomplete which may influence the PK analysis. Excluded cases will be documented together with the reason for exclusion. All decisions on exclusions from the analysis will be made prior to database closure.
Pharmacodynamic	All patients who had at least one pre-dose and one post-dose pharmacodynamic assessment will be included and analyzed.

ITT=intent-to-treat; NR=no response; PK=pharmacokinetic.

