6.1.1 Pre-medication and Prophylaxis

Nausea and vomiting have been commonly observed in idasanutlin studies. In some cases, they have led to treatment discontinuation.

- *Treatment to mitigate emesis must be given prophylactically prior to each cycle as follows: At least 30–60 minutes (timing depending on use of transdermal or oral 5-HT₃-receptor antagonist [RA]) before start of a treatment cycle and on each treatment day for dexamethasone administer:*
 - *Long-acting 5-HT₃-RA orally or intravenously (IV) on Day 1 (preferably palonosetron IV 0.25 mg or oral 0.5 mg) 30–60 minutes prior to idasanutlin administration or granisetron transdermal system ≥24 hours to a maximum of 48 hours prior to idasanutlin administration*

If the above recommended 5-HT₃-RAs are not available, treatment with short-acting 5-HT₃-RAs (e.g., 8 mg ondansetron) is mandatory 30 minutes prior to intake of idasanutlin on all treatment days (an extra dose of 8 mg ondansetron can be taken if symptoms appear later on treatment days, with a minimum of 8 hours between ondansetron doses).

AND

- *Dexamethasone 12 mg orally/IV on Day 1 (30–60 minutes before idasanutlin), then 8 mg orally on Days 2–5*

Investigators are to choose IV/oral/transdermal system administration at their discretion.

- *Anticipatory nausea: If the patient experiences nausea during the first cycle, consider adding anxiolytics, like lorazepam, from Cycle 2 onwards.*
- *Additional prophylaxis on top of the long-acting 5-HT₃-RA and dexamethasone is allowed per site local guideline and experience.*

Decrease in intensity of prophylaxis following Cycle 1 may be utilized based on investigator discretion, in agreement with the Medical Monitor, and patient tolerability.

All premedications for prophylaxis and on-study modifications should be captured on the patient's concomitant medications eCRF, indicating as intended for prophylaxis. The adverse GI events in the Phase I idasanutlin studies primarily included nausea, *diarrhea*, vomiting, abdominal pain, constipation, and anorexia. Supportive therapies for diarrhea and nausea are encouraged in this study.

See Section 8.3.9 for guidance for management of AEs and prophylaxis in subsequent cycles.

Re-dosing of study medication after emesis:

If vomiting occurs within 15 minutes of administering study medication and whole tablets are still intact, another dose may be administered, and the second dose must be

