7.1 DISCONTINUATION OF STUDY TREATMENT

Patient must discontinue study treatment if they experience any of the following:

- Pregnancy
- Unacceptable toxicity as determined by Investigator.
 - For cardiac changes:

If a clinically significant finding is identified (including, but not limited to QTcF ≥ 500 ms and/or an increase of ≥ 60 ms in QTcF from screening), the Investigator or qualified designee will determine if the patient can continue in the study and if any change in clinical management is needed. This review of the ECG printed at the time of collection must be documented. Any new clinically relevant finding should be reported as an AE.
- Any medical condition that the Investigator or Sponsor determines may jeopardize the patient's safety if he or she continues in the study.
- Investigator or Sponsor determines it is in the best interest of the patient.
- Disease progression at any point ([Appendix 1](#)).

Study treatment may be discontinued due to non-compliance (e.g., consistent failure to show up for scheduled visits) or if no evidence of clinical benefit in the form of lack of achieving a CR or PR per the ELN 2009 criteria, lack of achieving a Hct response or lack of decreased phlebotomy requirement at Week 32 assessment (see [Appendix 1](#)).

Patients who discontinue study treatment prematurely will be asked to return to the clinic for a study completion/early termination visit (see Section [8.9.3](#)) and may undergo follow-up assessments (see Section [8.9.4](#)). The primary reason for premature study treatment discontinuation should be documented on the appropriate eCRF. Patients

who discontinue study treatment prematurely for reasons other than progression or NR (withdraw prior to Week 32) may be replaced.

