7.2 WITHDRAWAL FROM THE STUDY

Patients have the right to voluntarily withdraw from the study at any time for any reason.

In addition, the Investigator has the right to withdraw a patient from the study at any time. Reasons for withdrawal from the study may include, but are not limited to, the following:

- Any medical condition that the Investigator or Sponsor determines may jeopardize the patient's safety if he/she continues in the study.

- Investigator or Sponsor determines it is in the best interest of the patient.
- Patient non-compliance.

If possible, information on reason for withdrawal from the study should be obtained. The primary reason for withdrawal from the study should be documented on the appropriate eCRF. Patients will not be followed for any reason after consent has been withdrawn.

When a patient voluntarily withdraws from the study, or is withdrawn by the Investigator, samples collected until the date of withdrawal will be analyzed, unless the patient specifically requests for these to be discarded or local laws require their immediate destruction. A patient's withdrawal from this study does not, by itself, constitute withdrawal of specimens donated to the Research Biosample Repository (RBR).

Patients who withdraw from the study after Week 32 assessments will not be replaced. Patients who withdraw prior to Week 32 from the study for reasons other than NR or PD may be replaced.

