3. FILTERS, POPULATIONS AND SUBGROUPS

Filter Category	Label of population or subgroup	Filter	Description
Main Populations	Safety-Evaluable Patients	SE	All patients who received at least one dose of the study treatment, whether prematurely withdrawn from the study or not, will be included in the safety analysis.
	Intent-to-Treat Patients	IT	All enrolled patients, regardless of previous ruxolitinib treatment
	Primary Efficacy Patients	PE	Ruxolitinib-naive patients both with splenomegaly by imaging or without splenomegaly who have Completed at least 32 weeks of treatment or withdrew prior to Week 32 due to NR or progressive disease.
	Early-Look Efficacy Patients	ELE	Patients who have completed at least 3 and/or 5 cycles

	PK Patients	PK	All patients who have received at least one dose of study treatment and who have data from at least one post-dose sample will be included in the PK analysis population. Patients will be excluded from the PK analysis population if they significantly violate the inclusion or exclusion criteria, deviate significantly from the protocol, or if data are unavailable or incomplete which may influence the PK analysis. Excluded cases will be documented together with the reason for exclusion. All decisions on exclusions from the analysis will be made prior to database closure.
	Pharmacodynamic Patients	PD	All patients who had at least one pre-dose and one post-dose pharmacodynamic assessment will be included and analyzed.
	Prior Rux exposed patients	RUX	
	Patients with splenomegally	SPLNML	All patients with splenomegaly
	Patients without splenomegally	WOSPLML	
	All Rux naïve	RUXNAIVE	
Sub-setting of data by patient characteristics – key subgroups only	Patients aged >= 65	AGEGE65	Patients aged 65 or more

Additional filters are used to subset data based on assessments, e.g. serious adverse events or assessments during treatment.

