5.7 Efficacy Analysis

5.7.1 Primary endpoint Response rate: Hct Criteria

The primary endpoint will be evaluated based on *hematocrit control* on the following populations

- All Patients without prior ruxolitinib exposure without Splenomegaly
 - Response is defined HCT control i.e. ≤ 1 instance of phlebotomy eligibility between first dose and Week 8; and ineligibility for phlebotomy between week 8 and Week 32 based on CRF;
Definition of eligibility for phlebotomy: a Hct of $\geq 45\%$ that was $\geq 3\%$ higher than baNPseline level or a Hct of $> 48\%$.
- Patients without prior exposure to ruxolitinib with Splenomegally
 - Using composite:
 - HCT control
 - $\geq 35\%$ reduction in spleen volume (primary at Week 32) from baseline
- All patients without prior exposure to Ruxolinitib with or without splenomegally
 - HCT control
 - Using HCT control without phlebotomy Notes:

A summary table for the response rates will be provided (RSPT01). Only descriptive statistics are used. No formal testing is done in the study.

RSPT01

Overview of response rate
Primary Efficacy Evaluable Population {, subgroup}
Protocol: {base protocol}

Overall At Week 32	Ruxolitinib Naïve (N=xx)			Ruxolitinib Exposed (N=xx)			All Patients (N=xx)
	With Splenomegaly (N=xx)	Without Splenomegaly (N=xx)	All Patients (N=xx)	With Splenomegaly (N=xx)	Without Splenomegaly (N=xx)	All Patients (N=xx)	
HCT Control	xx (xx.x%)	xx (xx.x%)	xx (xx.x%)	xx (xx.x%)	xx (xx.x%)	xx (xx.x%)	xx (xx.x%)
95% CI	(x.xx, x.xx)	(x.xx, x.xx)	(x.xx, x.xx)	(x.xx, x.xx)	(x.xx, x.xx)	(x.xx, x.xx)	(x.xx, x.xx)
Not Evaluable (NE)	xx (xx.x%)	xx (xx.x%)	xx (xx.x%)	xx (xx.x%)	xx (xx.x%)	xx (xx.x%)	xx (xx.x%)
Missing	xx (xx.x%)	xx (xx.x%)	xx (xx.x%)	xx (xx.x%)	xx (xx.x%)	xx (xx.x%)	xx (xx.x%)
Composite Response %	NA	NA	xx (xx.x%)	NA	NA	xx (xx.x%)	xx (xx.x%)
95% CI	NA	NA	(x.xx, x.xx)	NA	NA	(x.xx, x.xx)	(x.xx, x.xx)
Not Evaluable (NE)	NA	NA	xx (xx.x%)	NA	NA	xx (xx.x%)	xx (xx.x%)
Missing	NA	NA	xx (xx.x%)	NA	NA	xx (xx.x%)	xx (xx.x%)

Patients were classified as "Not Evaluable" if all post-baseline response assessments were reported as not evaluable, or SD assessment occurring within xxx weeks from baseline/study entry.

Patients were classified as "Missing" if no post-baseline response assessments were available.

Notes

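### The primary efficacy set drops, and allows replacement of, patients who leave before Week 32 for toxicity, own choice or loss to follow-up, so the primary response rates overstate the rate in treated patients

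*Protocol*

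**What the plan says.** Protocol Table 10 defines the primary efficacy population as "patients who have completed at least 32 weeks of treatment or withdrew prior to Week 32 due to NR or progressive disease", and section 9.4.2 bases the efficacy analyses on the Table 10 populations. SAP section 3 repeats the rule but words it for one cohort only: "Ruxolitinib-naive patients both with splenomegaly by imaging or without splenomegaly who have Completed at least 32 weeks of treatment", or who left earlier for NR or progression. The primary table RSPT01 (SAP 5.7.1) is headed "Primary Efficacy Evaluable Population {, subgroup" and has columns for ruxolitinib-exposed patients as well.

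Replacement follows the same line. Section 7.1 says that patients "who discontinue study treatment prematurely for reasons other than progression or NR (withdraw prior to Week 32) may be replaced". Section 7.2 says: "Patients who withdraw prior to Week 32 from the study for reasons other than NR or PD may be replaced".

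Section 9.4.2 also counts patients whose missing assessments prevent evaluation as NR, and allows at most one missed scheduled Hct between Weeks 8 and 32. The SAP separately defines an Intent-to-Treat set, "All enrolled patients, regardless of previous ruxolitinib treatment", and uses it for response by visit, CHR and duration of response.

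For the ruxolitinib-resistant or intolerant cohort, section 9.2.2 states that "if the proportion of responders based on Hct control is above 30% in the ruxolitinib-resistant or intolerant cohort, the Sponsor may decide to enroll" about 40 more patients. It sizes the cohort in efficacy-evaluable patients but does not name the denominator of that proportion.

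**The concern.** Membership of the primary set depends on what happens after treatment starts. A patient who stops for intolerance is neither a completer nor an NR/PD withdrawal and so disappears from the denominator. The rule that missing means NR cannot help, because it acts only on patients already in the set. A drug that many patients could not tolerate would look no less effective in the primary table.

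The protocol expects such exits. Unacceptable toxicity is a mandatory reason to stop (section 7.1), and loss to follow-up is a withdrawal reason of its own (section 7.3). Of nausea and vomiting in idasanutlin studies, section 6.1.1 says: "In some cases, they have led to treatment discontinuation".

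The resulting rates are read against fixed minimum rates: 35% for composite response and 60% for Hct control in the ruxolitinib-naive cohort, and 30% for Hct control in the resistant or intolerant cohort. The 30% figure is linked to an expansion aimed at registration, in which the first 20 patients are pooled into the total of 60.

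**Working it through.** **The plan's own figures.** With exact binomial tails, P(≥7/20 | 40%) = 75.0% (stated 75%) and P(≥14/20 | 75%) = 78.6% (stated 79%). The six Clopper-Pearson limits in Table 9 reproduce. The prior behind the stated posteriors is not given. A uniform prior gives 80.0% for P(rate > 60% | 14/20), against the stated 80%, but does not match the other four. A Jeffreys prior comes within 2 points of all five. The sample-size arithmetic is not in dispute.

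**Direction.** Composite response and CHR need Week 32 values. Hct control needs the record to Week 32 with at most one scheduled value missed. An early leaver is therefore almost always a non-responder; a very late leaver judged on Hct control alone is the rare exception. Early NR/PD withdrawals, and non-responders who stay to Week 32, are already counted. The gap is confined to exits for other reasons.

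**Size of the inflation.** Let r be the true rate among all treated patients and d the fraction leaving before Week 32 for other reasons, all non-responders. The rate among evaluable patients is then r/(1−d). The factor 1/(1−d) is 1.05 at d = 5%, 1.11 at 10% and 1.25 at 20%. No d is given in the documents, so a range is shown.

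**The 30% criterion.** Enrol until 20 patients are evaluable. The number of exits K is negative binomial (20 evaluable patients, probability 1−d each) and the responders X are Binomial(20, r/(1−d)). Compare P(X/20 > 0.30) with P(X/(20+K) > 0.30) in the same trial:

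| True rate r | Exits d | Evaluable denominator | All-treated denominator |
|---|---|---|---|
| 30% | 5% | 45% | 45% |
| 30% | 10% | 52% | 48% |
| 30% | 15% | 59% | 49% |
| 30% | 20% | 67% | 49% |
| 25% | 10% | 31% | 28% |
| 25% | 15% | 37% | 29% |
| 25% | 20% | 44% | 28% |

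The mean number treated, 20/(1−d), is 23.5 at 15% and 25 at 20%.

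**Single results, with leavers added back as non-responders**
- 7/20 = 35.0% becomes 7/24 = 29.2% with 4 leavers, no longer above 30%.
- 14/20 = 70.0% becomes 14/24 = 58.3%, below the 60% minimum. The posterior probability of exceeding 60% falls from 80% to 41% (uniform prior) or from 82% to 43% (Jeffreys).
- The Table 9 row 27/60 = 45.0% has lower limit 32.1%. With 7 leavers it becomes 27/67 = 40.3%, lower limit 28.5%.
- 26/60 has lower limit 30.6%. With 9 leavers, 26/69 has lower limit 26.3%.
- Results further from a threshold do not flip: 8/20 becomes 8/24 = 33.3%, and 30/69 has lower limit 31.6%.

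**The case against.** The other side has several fair points.

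- **The exclusions are disclosed.** Protocol 9.6 tabulates discontinuations for reasons other than progression, and SAP 5.4 summarises who is excluded from each population. A reader could rebuild the all-treated denominator. This is true, but disclosure leaves the headline rate on the selected set.
- **An all-enrolled table exists.** The by-visit shell in SAP 5.7.1 shows Hct control and composite response with confidence intervals in the Intent-to-Treat set, at visits following the protocol schedule. This softens the point. But that table is not designated primary, and it does not say that leavers count as non-responders. The default in SAP 4.4, percentages on non-missing patients, could drop them again. RSPT01 has its own rows for missing and not-evaluable patients, which suggests a denominator of N, so for that table the conflict with section 9.4.2 needs only a clarifying sentence.
- **The decision is soft.** Nothing is tested, expansion is at the sponsor's discretion, and safety data on every dosed patient are weighed too. All of this stands. The harm to the expansion decision also depends on the 30% criterion using the evaluable set, which the protocol leaves open.
- **The exit rates are assumed.** The only PV data in the protocol, 12 patients in section 2.3, report no dose-limiting toxicities, and section 8.3.9 does not expect severe GI toxicity or thrombocytopenia at these doses. Exits may be few. A true rate of exactly 30%, which the protocol itself regards as worthwhile, is the sensitive case. At 25% the gap is 8 points at 15% exits and 3 points at 10%.
- **Counting leavers as failures is an estimand choice.** It is, for exits unrelated to drug or disease. But section 9.4.2 already makes that choice for missing data.

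**Conclusion.** The concern holds. Followed as written, the plan removes near-certain non-responders from the primary denominator, may replace them, and so reports rates about 1/(1−d) times those in treated patients. The effect on the 30% criterion is negligible at 5% exits, about 4 points at 10%, and 10 to 18 points at 15–20% when the true rate is 30%. Results near a threshold can cross it; results well clear of it do not.

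The size rests on three assumptions: the exit fraction, which the documents do not give; leavers being non-responders; and, for the expansion decision, the criterion using the evaluable set. The direction rests only on the second, which the response definitions make close to certain.

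**What to change.** - In protocol Table 10 and section 9.4.2, make all patients with at least one dose in each cohort (the existing Safety definition) the primary efficacy set. Count any withdrawal before Week 32, for any reason, and any non-evaluable endpoint as non-response.
- In section 9.2.2, name this set as the denominator of the 30% expansion criterion.
- In sections 7.1 and 7.2, add one sentence saying that replaced patients stay in the denominator.
- In SAP section 3, word the primary set for both cohorts. In SAP 4.4 and 5.7, state that response percentages use N, consistent with missing counted as NR, and say how leavers are coded in the Intent-to-Treat tables.
- Keep the current evaluable set as a sensitivity analysis.

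The cost is wording only, with no new data or patients. Enrolment targets and the trigger for the primary analysis can stay on evaluable patients. The one downside for the sponsor is that reported rates will be somewhat less favourable.
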